Hypothesis 1b: Participants who remit with IPT or combination treatment will have fewer relapses over follow-up than those who remit with fluoxetine.

Aim 2:

Investigate key presumed mediators of the relationship between treatment and remission

Hypothesis 2a: For initial treatment with IPT, change in social support will mediate the relationship between treatment and remission—improved social support will be associated with remission

Hypothesis 2b: For initial treatment with fluoxetine, change in emotional reactivity will mediate the relationship between treatment and remission—decreased emotional reactivity will be associated with remission.

Aim 3: Identify demographic and clinical moderators of the relationship between treatment and remission.

Hypothesis 3a: Time or cost for transport between participants' residences and KCH, and other Kisumu County Ministry of Health facilities will moderate the relationship between treatment and remission—higher time/cost will decrease the effect of initial treatment with IPT relative to fluoxetine (more treatment visits required for IPT versus fluoxetine treatment).

Hypothesis 3b: Severity of MDD and/or PTSD symptoms among non-remitters will moderate the relationship between subsequent treatment and remission, such that higher severity will decrease the effect of treatment on remission for treatment switch relative to treatment combination.

Hypothesis 3c: Q learning will produce personalized treatment algorithms using the above or other moderators.

Aim 4. Estimate the costs and cost-benefit ratios for fluoxetine and IPT treatment of depression and PTSD.

Hypothesis 4a: Pooled cost-benefit ratios will show that depression and/or PTSD treatment leads to net economic gain for individuals and households at month 6;

Hypothesis 4b: Separate analyses will find that IPT has a more favorable cost-benefit than fluoxetine at month 30.

Aim 5. Determine the acceptability and feasibility of delivering SMART-DAPPER treatments by telephone.

Hypothesis 5a. Telephone IPT will be acceptable and feasible.

Hypothesis 5b. Telephone fluoxetine provider appointments will be acceptable and feasible.

Aim 6. Determine the effect of telephone treatment delivery on retention in care.

Hypothesis 6a. Participants who elect to receive telephone treatment will have higher retention in care than those who receive face-to-face care.

Significance

The results of the proposed research will be significant in two ways:

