Cost-benefit analyses. An important question for policymakers concerns the economic returns to investments in treating and improving mental health. We will use data obtained on the economic status of those treated to calculate the economic benefits associated with treated mental health disorders (both pooled analyses of IPT or fluoxetine treatment and separate analyses of IPT and fluoxetine treatment). We will also incorporate data on health care utilization and hospitalizations (Table 1). The value of these economic benefits will be summarized on a per-person basis and then combined with the implementation cost data to generate a rate of return on mental health expenditures (in general and by treatment type –IPT or fluoxetine). This rate of return is net gains in all economic measures divided by implementation costs, x 100 to yield % return. Cost and income measures will be adjusted for inflation and discounting during the 3 year study period.

Human participants in the project

Target population. Adult primary care outpatient clinic attendees at Kisumu County Hospital (KCH) and other Kisumu County Ministry of Health facilities.

Sample size calculations: SMART designs are used to inform the construction of optimal Adaptive Treatment Strategies (ATS), which is our goal. Therefore, we will power our study to detect the smallest difference between the various ATS included in the study design. The proposed SMART examines (1) first line treatment strategies with IPT or fluoxetine, including long-term relapse risk for participants who remit with initial treatment and (2) second line treatment strategies for non-remitters—specifically, treatment “switch” (from IPT to fluoxetine or vice versa) versus treatment “combination” (addition of IPT to fluoxetine or vice versa). Based on the current evidence base, we

expect that differences between switching or combining treatment will be smaller than other ATS comparisons in the study and we will therefore power the study to detect this difference.

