As it pertains to antidepressants and psychotherapy, the evidence base comparing “switching” versus “combining” treatment for non-remitters (second line treatment) is still developing. However, the field does have meta-analytic data on the differences between treating depression with antidepressants or psychotherapy alone, versus their combination. A 2009 meta-analysis (n=2036) which compared combination treatment (psychotherapy and pharmacotherapy) to pharmacotherapy alone for depression found an effect size of 0.31 (Cohen’s d).²⁷ A 2007 meta-analysis (n=903) found that the remission rate for major depression treated with psychotherapy and pharmacotherapy was better than psychotherapy alone, with an odds ratio of 1.5928, which when converted to a Cohen’s d is 0.25.²⁹ While specific studies have not yet been completed for IPT and PTSD, we leveraged the above-referenced meta-analyses of the effects of general psychotherapy and general pharmacotherapy to estimate sample size for the proposed study. Based on those studies, we would need approximately 164 per treatment arm to compare combined psychotherapy-medication treatment with medication alone, and 242 to compare combined psychotherapy-medication with psychotherapy, alone (using a two-sided alpha of 0.05 and power of 0.80). Using the conservative estimate, we will need 242 for each of the four treatment arms (968, total) after the second randomization (switch to fluoxetine, switch to IPT, combination after fluoxetine, combination after IPT). Note, this strategy uses fluoxetine treatment for 6 months as a first line treatment,

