Project Title: SMART-DAPPER: Leveraging the Depression And Primary-care Partnership for Effectiveness-implementation Research Project (SMART-DAPPER)

Clinicaltrials.gov number: NCT03466346

Title of Document: Statistical Analysis Plan

Date of Document: October 27, 2021

Statistical Analysis Plan

We used an intent-to-treat analysis. We used multivariate normal multiple imputation with 100 imputations to impute missing values of BDI-2 and PCL-5. For both of our primary outcomes (binary) we used generalized estimating equations (GEE) methods to fit a log-link binomial regression model with robust standard errors and a working exchangeable correlation structure to accommodate the repeated measures over time. Because not all participants had both major depression and PTSD at baseline, our analysis models the change in the risk of the outcome from baseline to end of first-line treatment.

Correspondingly, our model included the predictors of time (e.g., baseline and end of treatment), intervention group, the interaction of time, and intervention group. Results are described in terms of relative risks, and, for the interaction, ratios of relative risks with corresponding confidence intervals. The primary test of interest is the time by group interaction.

Secondary outcomes (BDI-2, PCL-5 continuous scores) were numeric, continuous variables. For these analyses we used GEE methods to fit a linear regression model with robust standard errors and a working exchangeable correlation structure. As before, our model included the predictors of time (baseline, end of treatment), intervention group and the interaction of time and intervention group. Results are described in terms of differences in mean values and, for the interaction, differences of differences with corresponding confidence intervals. The primary test of interest is the time by group interaction.

Participants who were not in remission at end of first line treatment were re-randomized to either treatment switch or treatment combination. These randomized comparisons were conducted using Fisher's exact test for MDD or PTSD or an exact Wilcoxon rank-sum test for BDI-2 score or PCL-5 score.

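### The second-line comparison that sets the sample size has only unadjusted exact tests, with no effect measure, confidence interval or imputation rule

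*SAP*

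**What the plan says.** - **Sizing.** The protocol (Sample size calculations) expects switch versus combination to be the smallest difference between strategies and says "we will therefore power the study to detect this difference". The result is that "we will need 242 for each of the four treatment arms (968, total) after the second randomization".
- **Second-line analysis.** The last paragraph of the SAP says only that non-remitters were re-randomised and compared by Fisher's "exact test for MDD or PTSD or an exact Wilcoxon rank-sum test for BDI-2 score or PCL-5 score". It mentions no covariate, first-line arm, effect measure or confidence interval.
- **Missing data.** The SAP's opening states intention to treat and "multivariate normal multiple imputation with 100 imputations to impute missing values of BDI-2 and PCL-5". It does not say whether this covers second-line outcomes, whether diagnoses are derived from imputed scores, or how an exact test is combined over 100 data sets.
- **Contrast with first line.** The same SAP gives the first-line comparison a GEE model with relative risks or mean differences and confidence intervals. The protocol's Data analysis plan makes logistic regression its basic strategy and includes BDI and PCL severity for Hypothesis 1a.
- **Hypothesis 3b.** The protocol expects that "Severity of MDD and/or PTSD symptoms among non-remitters will moderate the relationship between subsequent treatment and remission". The SAP contains no analysis of this.

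**The concern.** The comparison that fixed the size of the trial gets the thinnest analysis in the SAP. BDI-2, PCL-5 and MDD/PTSD status at the end of first-line treatment are the natural baseline for the second stage. The SAP already analyses them as first-line outcomes, so they are in hand. It also explains that the first-line model works with change from baseline because not everyone had both disorders at entry. Non-remitters may likewise have only one of the two disorders, yet the second-line tests use neither prior status nor prior score.

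Two things are at stake. One is precision. The other is that, as written, the plan would yield a p-value for switch versus combination without committing to a size of effect. Policy makers choosing between the two strategies need an estimate with an interval. Leaving the imputation rule open also leaves room to choose among results.

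**Working it through.** **Inputs from the protocol.** Calculations are made "using a two-sided alpha of 0.05 and power of 0.80". For combination versus medication, the meta-analysis of combined treatment against pharmacotherapy "alone for depression found an effect size of 0.31". For combination versus psychotherapy, the comparison comes "with an odds ratio of 1.5928, which when converted to a" Cohen's d of 0.25. I read the printed figure as 1.59 followed by a reference number (assumption; 1.5928 taken literally gives 239–240 per arm).

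**Assumed, because the documents give no values.** Switch-arm remission 30–60%; correlation ρ between score at re-randomisation and second-line score 0.3–0.6.

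**1. The plan's own figures.**
- d = ln(1.59) × √3/π = 0.4637 × 0.5513 = 0.2557.
- n per arm = 2(1.960 + 0.842)²/d² = 15.70/0.0654 = 240.1, so 241. The t-based version gives 241.1, so 242, as stated.
- For d = 0.31, 15.70/0.0961 = 163.3, so 164, as stated.
- 242 × 4 = 968.

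So 242 per arm is a two-mean calculation for a contrast within one first-line arm.

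**2. Scores, 242 versus 242.** Power = Φ(d√(n/2)/√(1−ρ²) − 1.96), with d√(n/2) = 0.2557 × 11 = 2.81.

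| Analysis | Power |
|---|---|
| Unadjusted means | 80.3% |
| Rank-sum (n × 0.955, normal scores) | about 78% |
| ANCOVA, ρ = 0.3 | 83.8% |
| ANCOVA, ρ = 0.4 | 86.6% |
| ANCOVA, ρ = 0.5 | 90.1% |
| ANCOVA, ρ = 0.6 | 94.0% |

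**3. Diagnoses, 242 versus 242, odds ratio 1.59 (exact enumeration).**

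| Switch | Combination | Fisher | Uncorrected chi-square |
|---|---|---|---|
| 30% | 40.5% | 64.8% | 68.3% |
| 40% | 51.5% | 68.5% | 71.7% |
| 50% | 61.4% | 68.0% | 71.2% |
| 60% | 70.5% | 64.4% | 67.9% |

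Fisher's actual type I error is about 0.04. At 50% versus 61.4%, simulated logistic regression adjusted for severity has 73%, 76% or 81% power for assumed slopes of 0.5, 0.8 or 1.1 log-odds per SD (3,000 replicates). About 3 points of the gain over Fisher come from leaving the conservative test (71.2 − 68.0). Adjustment adds about 2, 5 or 10 points.

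**4. Pooled over first-line arms, 484 versus 484.** Fisher power is 92–94% over the same remission range. For scores, d√(n/2) = 0.2557 × 15.56 = 3.98, so unadjusted power is 97.8%, and rank-sum power is about 97%. Adjustment multiplies the interval width for scores by √(1−ρ²): 0.95, 0.87 and 0.80 for ρ = 0.3, 0.5 and 0.6.

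**5. With the planned 40% dropout taken as losses from 2710.** 2710 × 0.6/2/4 = 203 per arm. Within a first-line arm, Fisher has 57–61%, unadjusted means 73.1% and ANCOVA 77.0–89.6%. Pooled (406 versus 406), Fisher has 87–90% and rank-sum about 95%.

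**6. Why an imputation rule is needed.** In one simulated data set with 20% missing and 100 imputations, Fisher p-values ran from 0.0004 to 0.198 across imputations. Rubin's rules on the log odds ratio gave a single answer, OR 1.53 (95% CI 1.03–2.27).

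**The case against.** The best defence is that unadjusted tests of a randomised comparison are valid and unbiased, so adjustment is a matter of efficiency. That stands. The SAP also does not say that the tests are run within first-line arm. If they pool both arms, power is already above 90% for the planned numbers and effect, and little is lost. That stands too; the four arms of 242 make the within-arm reading plausible, not certain. Everyone re-randomised is a non-remitter, so the range of severity is restricted, and the lower correlations and slopes are the more credible ones.

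A reader might go further in four ways that the documents do not support:
- **That the tests cannot be combined over imputations.** Rubin's rules need an estimate and a standard error and do not apply directly to exact p-values. Other combining rules exist, such as the median p-value. The gap is that none is stated.
- **That the tests give no effect estimate.** A conditional odds ratio with exact interval can accompany Fisher's test, and a Hodges–Lehmann shift the rank-sum test. The SAP specifies neither.
- **That second-line analysis is on completers.** The SAP does not say so. Its intention-to-treat and imputation statements are not limited to first line; whether they extend to second line is unclear.
- **That these tests fail Hypothesis 3b.** They do not claim to test it. The missing moderator model is a separate omission, although one regression can cover both.

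**Conclusion.** The concern holds as a loss of precision and a gap in specification. It is not a fault of validity, and nothing here suggests that the planned comparison would be biased.

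The size depends on the level of analysis. Within a first-line arm, where the 242 was set, the SAP's tests have about 64–69% power (diagnoses) and 78% (scores), against the planned 80%. ANCOVA would bring scores to about 84–94%. For diagnoses the gain is smaller and partly comes from dropping Fisher's test. Pooled over first-line arms, power is about 92–97% without adjustment, and the benefit is mainly a narrower interval.

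These figures rest on an odds ratio of 1.59, on the assumed remission rates, correlations and slopes, and on normal scores for the rank-sum figure. The absence of an effect measure, interval, first-line-arm term and imputation rule rests on no assumption.

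**What to change.** Make the main second-line analysis a regression on all re-randomised participants, with second-line arm, first-line arm, and BDI-2/PCL-5 score and MDD/PTSD status at re-randomisation.

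- **MDD and PTSD:** logistic or modified Poisson regression, reporting a standardised risk difference with 95% CI.
- **BDI-2 and PCL-5:** ANCOVA, reporting a mean difference with 95% CI.
- **Missing data:** state that imputation covers second-line outcomes and how missing diagnoses are obtained; pool estimates by Rubin's rules.
- **Within first-line arm:** also report the estimates separately after IPT and after fluoxetine, because the sample size was set at that level.
- **Hypothesis 3b:** add an arm-by-severity term to the same model.
- **Sensitivity:** keep Fisher's and the rank-sum tests.

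The cost is SAP text and a little more analysis work; no new data are needed. The SAP is written in the past tense. If second-line results are already known, label the adjusted analysis as added afterwards and report it beside the exact tests.
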